7.2. Clinical Laboratory Tests

All clinical laboratory reports will be displayed for the subjects included in the safety analysis set. The clinical laboratory parameters to be evaluated by the central laboratory include but are not limited to:

- **Hematology:** hemoglobin, hematocrit, lymphocytes, neutrophils, platelets, red blood cell (RBC) count and white blood cell (WBC) count.
- **Chemistry:** albumin, alkaline phosphatase, alanine aminotransferase, aspartate aminotransferase, total carbon dioxide (CO₂), total bilirubin, blood urea nitrogen/urea, calcium, chloride, creatinine, glucose, potassium, total protein, sodium.

Descriptive statistics for selected clinical laboratory analyte and for change from baseline at each scheduled post-baseline visit through Week 16 will be provided by treatment group for Part 1. Box plots of laboratory measurements and change from baseline through Week 52 will be provided for selected laboratory analytes.

Applicable laboratory results will be graded according to National Cancer Institute's Common Terminology Criteria for Adverse Events (NCI-CTCAE version 4.03). The proportion of subjects with post-baseline values by maximum toxicity grade for clinical laboratory tests will be summarized by treatment group.

For nonfasting glucose, the screening measurement will be used as the baseline measurement. A listing of subjects with 1 or more NCI-CTCAE toxicity grade ≥ 2 abnormalities in hematology and clinical chemistry laboratory measurements will be provided.

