**1.3. Schedule of Activities (SoA)**

**1.3.1. Screening Through Week 52 – Part 1a and 1b**

Phase	Screening a	Placebo-controlled					Withdrawal and Retreatment b										Study Termination Visit e
		0	4	8	12	16	20	24	28	32	36	40	44	48	52 d		
Study Procedurese																	
Screening/Administrative																	
Informed consent/assent f	X																
Medical history and demographics	X																
Inclusion/exclusion criteria	X	X															
Study Intervention Administration																	
Randomization		X															
Administration b,g,h,i,j		X-----															
Safety Assessments																	
Physical examination (including skin exam and Tanner staging)	X						X								X	X	
Vital signs k	X	X	X	X	X	X	X	X	X	X	X	X	X	X	X	X	
Tuberculosis evaluation	X	X	X	X	X	X	X	X	X	X	X	X	X	X	X	X	
Urine pregnancy test l	X	X	X	X	X	X	X-----										X
Height		X			X		X				X				X	X	
Weight	X	X	X	X	X	X	X	X	X	X	X	X	X	X	X	X	
Head circumference m		X													X	X	
Assessment of injection pain n		X	X		X	X	X	X	X	X	X	X	X	X	X		
C-SSRS o	X	X	X	X	X	X	X	X	X	X	X	X	X	X	X	X	
Concomitant therapy	X	X	X	X	X	X	X	X	X	X	X	X	X	X	X	X	
Adverse events	X	X	X	X	X	X	X	X	X	X	X	X	X	X	X	X	

Phase	Screening a	Placebo-controlled					Withdrawal and Retreatment b										Study Termination Visit c
		0	4	8	12	16	20	24	28	32	36	40	44	48	52 d		
Study Procedurese																	
Efficacy Assessments																	
IGA p	X	X	X	X	X	X	X	X	X	X	X	X	X	X	X	X	
PASI p	X	X	X	X	X	X	X	X	X	X	X	X	X	X	X	X	
Body surface area (BSA)% p	X	X	X	X	X	X	X	X	X	X	X	X	X	X	X	X	
Children’s Dermatology Life Quality Index (CDLQI) q		X		X		X			X		X			X	X	X	
Family Dermatology Life Quality Index (FDLQI) r		X		X		X			X		X			X	X	X	
Clinical Laboratory Assessment																	
QuantIFERON-TB test s	X																
Hepatitis B and C serology	X																
HIV antibody test	X																
Serum varicella, measles, mumps, and rubella antibody titers t	X																
Serum IgG, IgM, and IgA		X				X									X	X u	
Hematology v	X	X x		X		X			X		X		X		X	X	
Chemistry v,w	X	X x		X		X			X		X		X		X	X	

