**Table 1: Approximate Total Volume of Blood Per Type of Sample to be Collected Through Week 52 from Each Participant**

Type of Sample	Volume per Sample (mL)	No. of Samples per Participant	Approximate Total Volume of Blood (mL) a
Hematology	2	8	16
Serum chemistry	2.5	8	20
Serology (HIV, hepatitis)	6.5	1	6.5
Serum antibody titers for varicella, measles, mumps, and rubella b	2.5	1	2.5
QuantiFERON ® -TB testing	4	1	4
Pharmacokinetic samples only c	2.5	2	5
Pharmacokinetics and immunogenicity samples d	3.5	6	21
Serum immunoglobulin levels e	2.5	3	7.5
Approximate Total f			82.5

a. Calculated as number of samples multiplied by amount of blood per sample.

b. Titers for measles, mumps, rubella, and varicella only required if adequate documentation of complete vaccination schedule or healthcare provider verification of previous infection is unavailable.

c. Blood samples collected for pharmacokinetics only evaluation (approximately 2.5 mL each): each serum sample will be split into 2 aliquots (approximately 0.5 mL each).

d. Blood samples collected for pharmacokinetic and immunogenicity evaluations (approximately 3.5 mL each): each serum sample will be split into 3 aliquots (approximately 0.5 mL each).

e. IgG, IgM, IgA

f. Repeat or unscheduled samples may be taken for safety reasons or technical issues with the samples.

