7. SAFETY

Safety will be assessed by summarizing the incidence and type of AEs and examining changes in laboratory parameters (hematology and chemistry), vital signs, and suicidal ideation and behavior.

In the safety analyses for Part 1, subjects who were randomized and received at least 1 (partial or complete) dose of study agent administration will be included and analyzed according to the treatment they actually received, regardless of the treatment assigned at randomization. No formal statistical comparison is planned.

For Part 2, the safety analyses will be performed for all subjects enrolled in Part 2 and treated.

For LTE, the safety analyses will be performed for all subjects entered in LTE and treated at or after Week 52.

Depending on the safety data categories, the cumulative safety data will be analyzed through different study periods which include but are not limited to through Week 16, through Week 52, and through the LTE as appropriate. Unless otherwise specified, tabular summaries of safety events for key study periods are in general presented as follows:

Summaries through Week 16 (placebo-controlled period in Part 1):

Safety data through Week 16 will be summarized by treatment groups:

- Placebo
- Guselkumab
- Etanercept

This allows between-group comparisons of safety between the guselkumab group, etanercept group and the placebo group based on similar follow-up period in each group.

Summaries through Week 52 in Part 1

Safety data through Week 52 will be summarized by treatment group defined as follows:

1. **Placebo → Guselkumab:** all subjects who were randomized to placebo at Week 0, started treatment with placebo only, and later crossed over to receive treatment with guselkumab. Only the safety events/measurements from these subjects that occurred on or after their first administration of guselkumab will be included in this group.

2. **Guselkumab:** all subjects who were randomized to guselkumab at Week 0 and were treated with guselkumab. All the safety events/measurements from these subjects that occurred beginning at Week 0 will be included in this group.
3. **Etanercept → Guselkumab:** all subjects who were randomized to etanercept at Week 0, started treatment with etanercept only, and later crossed over to receive treatment with guselkumab. Only the safety events/measurements from these subjects that occurred on or after their first administration of guselkumab will be included in this group.

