7.1. Adverse Events

The verbatim terms used in the CRF by investigators to identify adverse events will be coded using the Medical Dictionary for Regulatory Activities (MedDRA version xx). Any AE occurring at or after the initial administration of study agent through the end of the trial is considered to be treatment emergent. If the event occurs on the day of the initial administration of study agent, and either event time or time of administration are missing, then the event will be assumed to be treatment emergent. If the event date is recorded as partial or completely missing, then the event will be considered to be treatment emergent unless it is known to be prior to the first administration of study agent based on partial onset date or resolution date. All reported treatment-emergent adverse events will be summarized by MedDRA system organ class, preferred term, and actual treatment group. The numbers of subjects reporting at least 1 event of the following treatment emergent AE categories will be summarized.

- AEs
- Serious AEs (SAEs)
- AEs leading to discontinuation of study agent

- AEs by severity
- AEs by relationship to study agent
- Infections
- Serious infections
- Infections treated with oral or parenteral antimicrobial treatment
- Injection-site reactions

In addition to the summary tables, listings will be provided for subjects who:

- Had SAEs
- Had AEs leading to discontinuation of study agent
- AEs of psoriasis
- AEs of severe intensity
- Serum sickness-like reactions and anaphylactic reactions

These summary tables will provide the count and percentage of subjects with 1 or more of the specified AEs by treatment group. The AEs and infections will also be summarized by age group through Week 16 and through Week 52 for Part 1. To adjust for the different duration of follow-up among treatment groups, number of events per hundred subject-years of follow-up through Week 52 will also be provided for all AEs.

Any unfavorable or unintended sign that occurs at the injection site is an injection site reaction and will be recorded as an injection site reaction by the investigator on the eCRF. An infection is defined as any AE that was recorded as an infection by the investigator on the eCRF.

The treatment-emergent adverse events of psoriasis include any event of erythrodermic psoriasis, pustular psoriasis, guttate psoriasis, and worsening or exacerbation of psoriasis. A listing of these events will be provided.

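### The Part 1 Week 52 table of maximum laboratory toxicity grade sets groups with six scheduled draws beside groups with about four, and the SAP makes no allowance for it

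*SAP*

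**What the plan says.** SAP 7.2 grades laboratory results by NCI-CTCAE and then states: "The proportion of subjects with post-baseline values by maximum toxicity grade for clinical laboratory tests will be summarized by treatment group". The sentence gives no study period. Elsewhere in 7.2, the by-visit descriptive statistics stop at Week 16, box plots of selected analytes run to Week 52, and participants with grade 2 or higher values are listed.

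The periods come from SAP 7: "Unless otherwise specified, tabular summaries of safety events for key study periods are in general presented as follows". The Week 16 summaries come first, then: "Safety data through Week 52 will be summarized by treatment group defined as follows". The Week 52 groups do not share a counting window:

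- Guselkumab: "All the safety events/measurements from these subjects that occurred beginning at Week 0 will be included in this group".
- Placebo → Guselkumab and Etanercept → Guselkumab: "Only the safety events/measurements from these subjects that occurred on or after their first administration of guselkumab will be included in this group".
- Combined Guselkumab pools all three.

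For adverse events, SAP 7.1 deals with the unequal windows: "To adjust for the different duration of follow-up among treatment groups, number of events per hundred subject-years of follow-up" are to be given through Week 52. Most adverse event tables will also show average follow-up and average number of administrations. SAP 7.2 has no counterpart for laboratory grades.

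**The concern.** The percentage of participants whose worst grade reaches a given level depends on how often they are sampled. Each extra draw is another chance to record an abnormal value, and none can lower the maximum. If one column is built on six draws and its neighbours on four, the columns differ even when guselkumab has the same effect in all of them.

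A reader could take a higher percentage in the Guselkumab column as a signal from earlier or longer exposure when part of it is extra sampling. The Combined Guselkumab column blends participants with different chances of detection, so its percentage has no clear denominator in time or samples. Safety is part of the primary objective, and this is the main tabulated summary of laboratory grades over the year.

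**Working it through.** **Inputs**

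- Draw schedule: Protocol 1.3.1, hematology and chemistry rows (same pattern).
- Stated sample count: Protocol Section 8, Table 1.
- First guselkumab dose: Week 16 for placebo PASI 90 nonresponders, Week 20 for etanercept participants who switch, and on loss of response for placebo PASI 90 responders (Protocol 1.3.1, footnotes h, i and b).
- Sampling precedes dosing at dosing visits (Protocol 1.3.1, footnotes e and y).
- Per-draw risk p and within-person correlation (ICC): not in the documents. Assumed p = 0.1% to 30% and ICC = 0 to 0.7.

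**Reproducing the plan's own count.** The scheduled draws through Week 52 are screening and Weeks 0, 8, 16, 28, 36, 44 and 52, which is 8. Table 1 has the same: "Hematology 2 8 16" (2 mL × 8 samples = 16 mL), with 8 for chemistry too. The termination-visit draw is left out.

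**Draws per group in a Week 52 table**

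| Group | Draws counted | Number |
|---|---|---|
| Guselkumab | 8, 16, 28, 36, 44, 52 | 6 |
| Etanercept → Guselkumab (from Week 20) | 28, 36, 44, 52 | 4 |
| Placebo → Guselkumab, nonresponders, Week 16 pre-dose sample excluded | 28, 36, 44, 52 | 4 |
| Same, Week 16 sample counted by date | 16, 28, 36, 44, 52 | 5 |
| Placebo PASI 90 responders starting at Week 28 or 32 | 36, 44, 52 | 3 |
| Same, starting later | from 44 or only 52 | 2 or 1 |

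**Independent draws.** The chance of at least one graded value in m draws is 1 − (1 − p)^m.

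| p per draw | 6 draws | 5 draws | 4 draws | Ratio 6:4 | Ratio 6:5 |
|---|---|---|---|---|---|
| 1% | 5.9% | 4.9% | 3.9% | 1.49 | 1.19 |
| 2% | 11.4% | 9.6% | 7.8% | 1.47 | 1.19 |
| 5% | 26.5% | 22.6% | 18.5% | 1.43 | 1.17 |
| 7% | 35.3% | 30.4% | 25.2% | 1.40 | 1.16 |
| 10% | 46.9% | 41.0% | 34.4% | 1.36 | 1.14 |
| 20% | 73.8% | 67.2% | 59.0% | 1.25 | 1.10 |
| 30% | 88.2% | 83.2% | 76.0% | 1.16 | 1.06 |

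As p falls towards zero the 6:4 ratio tends to 6/4 = 1.5, which is its ceiling (1.499 at p = 0.1%).

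**Correlated draws.** In a beta-binomial model with ICC ρ, a = p(1 − ρ)/ρ and b = (1 − p)(1 − ρ)/ρ. The chance of at least one graded value is 1 − ∏(b + i)/(a + b + i), for i = 0 to m − 1. The 6:4 ratio for p from 10% down to 1% is:

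- ICC 0.1: 1.30 to 1.38
- ICC 0.3: 1.21 to 1.25
- ICC 0.5: 1.15 to 1.17
- ICC 0.7: 1.10 to 1.11

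**Week 16 table.** All three arms have the same two post-baseline draws (Weeks 8 and 16), so the ratio is 1.

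**Would a rate help?** Scheduled draws per subject-year after first guselkumab are 6 × 52/52 = 6.0 for Guselkumab, 4 × 52/36 = 5.8 for placebo nonresponders and 4 × 52/32 = 6.5 for etanercept switchers. Draw density is nearly equal, so a rate per subject-year removes most of the unequal detection. Dividing abnormal samples by samples taken adjusts for the number of draws directly.

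**The case against.** **The table is inferred.** A reader might take 7.2 as explicitly calling for a Week 52 maximum-grade table. It does not: the period comes from defaults in SAP 7 that apply in general and as appropriate. The inference is still the natural one, because 7.2 limits the by-visit statistics to Week 16 and puts no such limit on the grade table.

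**The Week 52 columns are not meant for comparison.** SAP 7 attaches between-group safety comparison to the Week 16 summaries, where follow-up is similar, and plans no formal test. It is therefore right that no test or error rate is touched. But SAP 7.1 adjusts the Week 52 adverse event figures precisely because follow-up differs among groups, so the SAP itself expects those columns to be read side by side.

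**The size is uncertain.** A reader might quote a flat 1.4 to 1.5. That needs independent draws and a per-draw risk of about 7% or less. At 10% the ratio is 1.36, and an ICC of 0.1 already takes it below 1.4. The count of four for placebo nonresponders also depends on leaving out the Week 16 pre-dose sample, which the SAP wording does not settle. These points stand.

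**The net direction is unknown.** This is the strongest objection. Guselkumab PASI 90 responders have their last initial dose at Week 12 and are withdrawn until they lose response. If the adult PASI 90 rates in Protocol 2.2.1 (73.3% and 70.0%) carried over, which is an assumption, 40 × 0.700 = 28 to 40 × 0.733 = 29 of the 40 planned guselkumab participants would be withdrawn. Many of their later draws could be off drug, while crossover draws are on drug. A reader might conclude that the Guselkumab column must overstate toxicity overall; the documents do not support that. What can be said is that extra sampling by itself pushes that column up.

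**The practical size is modest.** With about 25 planned per crossover group, the 8.0-point gap at p = 5% is 25 × 0.080 = 2 participants, and the 2.0-point gap at p = 1% is half of one. The grade 2 or higher listing gives case detail, but neither it nor the box plots supplies a denominator for the percentage.

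**Conclusion.** The point holds as a matter of presentation. On the default reading of SAP 7, the Week 52 maximum-grade percentages rest on six scheduled draws in the Guselkumab group. They rest on four in Etanercept → Guselkumab and four in Placebo → Guselkumab nonresponders, or five for the latter if the same-day Week 16 sample is counted. Placebo PASI 90 responders can have fewer.

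At equal per-draw risk the sampling difference alone inflates the Guselkumab percentage by up to 1.5-fold for six versus four draws. The range is roughly 1.15 to 1.5 for per-draw risks up to 10% and ICC from 0 to 0.5, and lower with stronger correlation. Against five draws it is about 1.14 to 1.20 with independent draws. These sizes rest on assumed risks and correlations and on complete scheduled sampling.

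The SAP already accepts the principle for adverse events and leaves it out for laboratory grades. The severity is low because the table is descriptive.

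**What to change.** For the Part 1 laboratory toxicity table through Week 52:

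1. Keep the maximum-grade percentage and name the period in SAP 7.2.
2. Add, by group, the number of draws per participant after first guselkumab.
3. Add, by group, either participants with a first grade 2 or higher value per 100 subject-years after first guselkumab, or abnormal samples divided by samples taken.
4. State that samples taken before the first guselkumab dose on the same day are excluded from the crossover groups.
5. Footnote that the Guselkumab column includes off-drug withdrawal time after Week 16. The adjusted figures then correct for the opportunity to detect an abnormality and do not by themselves support an on-drug comparison.

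The cost is a few lines of SAP text and one extra table from data already collected. The downside is a slightly longer laboratory output.

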  - Hemoglobin  $\geq 10$  g/dL (SI:  $\geq 100$  g/L; 6 to 11 years of age)  
 $\geq 12$  g/dL (SI:  $\geq 120$  g/L;  $\geq 12$  years of age)
  - White blood cells  $\geq 3.0 \times 10^3$  cells/ $\mu$ L (SI:  $\geq 3.0 \times 10^9$  cells/L; 6 to 11 years of age)  
 $\geq 4.5 \times 10^3$  cells/ $\mu$ L (SI:  $\geq 4.5 \times 10^9$  cells/L;  $\geq 12$  years of age)
  - Neutrophils  $\geq 1.5 \times 10^3$  cells/ $\mu$ L (SI:  $\geq 1.5 \times 10^9$  cells/L)
  - Platelets  $\geq 150 \times 10^9$ /L
  - Serum creatinine  $\leq 0.7$  mg/dL (SI: 62  $\mu$ mol/L; 6 to 10 years of age)  
 $\leq 1.0$  mg/dL (SI: 88  $\mu$ mol/L; 11 to 12 years of age)  
 $< 1.5$  mg/dL (SI:  $< 133$   $\mu$ mol/L;  $> 12$  years of age)
  - Aspartate aminotransferase (AST)  $\leq 72$  IU/L (6 to 11 years of age)  
 $< 1.5 \times$  ULN for the laboratory conducting the test ( $\geq 12$  years of age)
  - Alanine aminotransferase (ALT)  $\leq 54$  IU/L (6 to  $< 18$  years of age)

If one or more of the above laboratory parameters is out of range, a single retest of laboratory values is permitted.

17. Must be willing and able to adhere to the prohibitions and restrictions specified in this protocol.
18. Must sign an ICF (or their legally acceptable representative must sign) indicating that he or she understands the purpose of, and procedures required for, the study and is willing to

participate in the study. Parent(s) (preferably both if available or as per local requirements) (or their legally acceptable representative) must sign an ICF indicating that he or she understands the purpose of, and procedures required for, the study and is willing to allow the child to participate in the study, as per local requirements. Assent is also required of children capable of understanding the nature of the study (typically 7 years of age and older) as described in Informed Consent Process in [Appendix 2](#) (Section 10.2), Regulatory, Ethical, and Study Oversight Considerations.

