### **7.1. Discontinuation of Study Intervention**

A participant's study intervention must be discontinued if any of the following occur:

- The investigator believes that for safety reasons or tolerability reasons (eg, AE) it is in the best interest of the participant to discontinue study intervention
- An AE temporally associated with study intervention injection, resulting in bronchospasm with wheezing and/or dyspnea requiring ventilatory support, or symptomatic hypotension (defined as systolic BP <  $[70 + (2 \times \text{age in years})]$ ).
- The participant or their legally acceptable representative withdraws consent/assent for administration of study intervention.
- Pregnancy, or pregnancy planned within the study period or within 12 weeks after the last study intervention injection.
- The initiation of protocol-prohibited medications or treatments as outlined in Section 6.5, Concomitant Therapy, unless agreed to by the sponsor medical monitor.
- The participant is diagnosed with a malignancy.

- An opportunistic infection.
- A recurrent or chronic serious infection.
- A severe study intervention injection-site reaction.
- The participant meets one of the following TB criteria:
  - A diagnosis of active or latent TB is made.
  - A participant has symptoms suggestive of active TB based on follow-up assessment questions and/or physical examination or has had recent close contact with a person with active TB and cannot or will not continue to undergo additional evaluation.
  - A participant undergoing evaluation has chest imaging with evidence of TB and/or a positive IGRA test result and/or 2 indeterminate/borderline IGRA test results. Indeterminate/borderline or suspected false-positive tests should be handled as outlined in Section 8.
- The participant has liver test abnormalities as described in Section 8.2.3 and Appendix 12 (Section 10.2). Such abnormalities would include the following:
  - ALT or AST >8 x ULN
  - ALT or AST >5 x ULN for more than 2 weeks
  - ALT or AST >3 x ULN **and** (total bilirubin >2 x ULN or international normalized ratio [INR] >1.5)
  - ALT or AST >3 x ULN **and** symptoms of hepatitis (eg, fatigue, nausea, vomiting, right upper quadrant pain or tenderness, fever, rash, and/or eosinophilia [>5%])
- The participant is unable to adhere to the study visit schedule or comply with protocol requirements.

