## Clinical Laboratory Tests

Laboratory data will be summarized by type of laboratory test. Descriptive statistics will be calculated for each laboratory analyte and changes from baseline at each scheduled time point. In addition, National Cancer Institute-Common Terminology Criteria for Adverse Events (NCI-CTCAE) grades will be used in the summary of laboratory data. A listing of participants with post-baseline abnormal laboratory results based on NCI-CTCAE grades will also be provided.

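### Laboratory toxicity is tabulated by worst post-baseline grade with no reference to baseline grade, so abnormalities present at entry are counted together with new ones

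*SAP*

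**What the plan says.** SAP 7.2 grades applicable results by NCI-CTCAE version 4.03 and plans two graded outputs. The table is defined as "The proportion of subjects with post-baseline values by maximum toxicity grade for clinical laboratory tests will be summarized by treatment group". The listing is defined as "A listing of subjects with 1 or more NCI-CTCAE toxicity grade ≥ 2 abnormalities in hematology and clinical chemistry laboratory measurements will be provided". Protocol 9.4.3 adds only that "A listing of participants with post-baseline abnormal laboratory results based on NCI-CTCAE grades will also be provided". None of these mentions the grade at baseline.

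Baseline enters laboratory reporting only through numeric values. SAP 7.2 plans "Descriptive statistics for selected clinical laboratory analyte and for change from baseline at each scheduled post-baseline visit through Week 16", by treatment group for Part 1, and "Box plots of laboratory measurements and change from baseline through Week 52 will be provided for selected laboratory analytes". Protocol 9.4.3 is broader: it promises descriptive statistics of values and changes for every analyte at every scheduled time point.

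On entry values, criterion 16 in Protocol 5.1 requires the following:
- AST from age 12: below 1.5 x "ULN for the laboratory conducting the test".
- AST at 6 to 11 years: at most 72 IU/L.
- ALT at all ages: at most 54 IU/L.
- Total bilirubin and alkaline phosphatase: no limit, although both are in the SAP chemistry panel.

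SAP 2.7 takes baseline as the last measurement up to the day of the first study agent dose. SAP 7 counts measurements for the two crossover groups only from the first guselkumab dose onward.

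**The concern.** A worst-grade count with no baseline condition answers the question of who had an abnormal value after baseline. A reader of a safety table usually wants to know who developed one or got worse. The two answers differ whenever participants can enter with a graded value, and criterion 16 allows this for AST in so many words.

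Taking a maximum over visits adds to the problem. Chemistry is drawn at Weeks 8, 16, 28, 36, 44 and 52 in both parts, so a single recurrence in six draws is enough to be counted through Week 52.

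The plan is stricter elsewhere. Protocol 9.4.3 treats an adverse event arising from a pre-existing condition as intervention-emergent only if the condition has worsened. The graded laboratory outputs carry no such condition.

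At stake is what can be read from the grade proportions where no concurrent arm shows the background rate: Part 2, the extension and the Part 1 crossover groups through Week 52. The crossover groups have a further difficulty. Their baseline precedes the first study agent, so an abnormality that arose on placebo or etanercept can be counted after the switch to guselkumab.

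**Working it through.** The documents state no figure for this table, so there is none to reproduce. The check has two parts.

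**1. Does eligibility admit values above normal?**
- AST from age 12: yes. Values from just above 1.0 to just below 1.5 x ULN are eligible on the document's own wording.
- The fixed limits depend on a ULN that is not given. For an assumed ULN of 30 to 60 IU/L, the ALT limit is 54/30 = 1.80 down to 54/60 = 0.90 x ULN, so it admits values above normal only if the ULN is below 54. The AST limit at 6 to 11 years is 72/30 = 2.40 down to 72/60 = 1.20 x ULN, above normal throughout that range.
- Bilirubin and alkaline phosphatase: criterion 16 does not bound the entry value.

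**2. How many participants could be counted without worsening?** Inputs from the documents are the planned arm sizes: guselkumab 30 + 10 = 40, placebo 15 + 10 = 25, etanercept 15 + 10 = 25. Assumed inputs are a prevalence of a graded baseline value of 5% to 20% for a given analyte, and a chance of 50% to 100% that it is still present or recurs after baseline. The product q therefore runs from 0.05 x 0.5 = 2.5% to 0.20 x 1.0 = 20%.

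Formulas:
- expected count = n x q
- chance of at least one in the guselkumab arm = 1 − (1 − q)^40
- SD of the chance difference between guselkumab and placebo = sqrt(q(1 − q)(1/40 + 1/25))
- the last column enumerates two independent binomials, with sizes 40 and 25

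| q | Expected of 40 | Expected of 25 | P(at least 1 of 40) | SD of difference, points | P(difference of 10 points or more, either way) |
|---|---|---|---|---|---|
| 2.5% | 1.0 | 0.6 | 0.64 | 4.0 | 0.02 |
| 5% | 2.0 | 1.2 | 0.87 | 5.6 | 0.08 |
| 10% | 4.0 | 2.5 | 0.99 | 7.6 | 0.20 |
| 20% | 8.0 | 5.0 | >0.99 | 10.2 | 0.34 |

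The expected proportion is q in every arm, so the expected difference to Week 16 is zero. Only the spread grows. In the combined guselkumab group through Week 52, if everyone in the other two arms crossed over, n = 40 + 25 + 25 = 90 and the expected count is 90 x 0.025 = 2.25 to 90 x 0.20 = 18. No concurrent group is available there to set against it.

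**The case against.** The strongest reply is that this is a layout matter in one descriptive table. SAP 7 plans no formal safety comparison, and the table is labelled post-baseline, not treatment-emergent. Baseline-referenced information also exists. The Protocol promises change from baseline for every analyte, and its section 9 defines descriptive statistics to include median, interquartile range and range, so extreme changes are visible as well as averages. Box plots run to Week 52, and all laboratory reports are to be displayed. Clinically relevant laboratory changes also reach the adverse event tables through the investigator.

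Most of this stands, and it rules out a reading that nothing in Part 2 separates old from new abnormality. It does not close the gap, because these outputs are numeric and none says whose grade rose. The SAP also narrows the Protocol's commitment to selected analytes and, for the descriptive statistics, to Part 1 through Week 16. It specifies no baseline-referenced laboratory output for the extension.

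A reader might also infer that the liver stopping rules are contaminated, since Protocol 7.1 lists as a reason to discontinue that "The participant has liver test abnormalities as described in Section 8.2.3 and Appendix 12". The documents do not support that. Every aminotransferase threshold there is above 3 x ULN or higher, and the bilirubin and INR conditions apply only together with an aminotransferase above 3 x ULN. A stable AST below 1.5 x ULN cannot reach this. The fixed limits could exceed 3 x ULN only with a ULN below 54/3 = 18 IU/L for ALT or 72/3 = 24 IU/L for AST.

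**Conclusion.** The point holds as a minor, cheaply corrected gap. The graded laboratory outputs count an entry abnormality that persists or recurs alongside new abnormality, and no planned output by grade separates them. The same gap applies to haematology.

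The size rests on two assumptions. One is that any value above ULN is at least grade 1. The other is the 2.5% to 20% range for a persisting or recurring entry abnormality, which has no source in the documents; its upper end needs 20% prevalence and full persistence. Under these assumptions, 1 to 8 of 40 guselkumab participants are counted without worsening. For AST and ALT the effect should lie mainly in the low grades. Criterion 16 does not bound it for bilirubin or alkaline phosphatase.

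Two stronger readings should be resisted. The randomized comparison to Week 16 is not biased: arms are affected equally in expectation, and small arms make the difference noisier. Nor is every entry abnormality reported as toxicity in every period: a value that normalizes and stays normal after baseline drops out. The practical consequence is for the Week 52 crossover groups, Part 2 and the extension.

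**What to change.** In SAP 7.2, keep the maximum-grade table and add wording such as: *For each graded analyte, a shift table of baseline grade by worst post-baseline grade, and the proportion of subjects whose worst post-baseline grade exceeds the baseline grade, will be presented by treatment group and study period. For subjects who cross over to guselkumab, baseline for the guselkumab period is the last value before the first guselkumab dose.* For placebo participants who start guselkumab at Week 16 and etanercept participants who start at Week 20, the scheduled chemistry and haematology draw that supplies this value is Week 16.

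Keep every participant in the grade 2 or higher listing and add a column for baseline grade. Replacing the table, or restricting the listing to grades that rose, would hide persistent grade 2 or higher values in a paediatric safety report and should be avoided.

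The cost is one additional table and minor programming. Baseline chemistry and haematology are already scheduled at screening and Week 0, with the screening value serving where the Week 0 draw is waived. No new samples, visits or clinical rules are involved.
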